## C. Subject Selection

### Subject Population

The study population will be all patients aged 21 to 85 years referred for prostate needle biopsy (both standard sextant and MRI-fusion guided) to BIDMC within 6 months' period. A total of 152 patients will be enrolled for the study.

### Eligibility Criteria

#### *Inclusion criteria:*

- (1) Biological male
- (2) Aged 21 to 85 years
- (3) Scheduled for prostate needle biopsy
- (4) No learning disabilities
- (5) Suitable for nitrous oxide/oxygen IHS with willingness to be randomized to inhaled SANO or inhaled oxygen during the procedure
- (6) Access to an email and computer

#### *Exclusion criteria:*

- (1) Perioral facial hair impeding good mask seal
- (2) Learning disabilities and/or inability to cognitively complete survey questions
- (3) Taken a pre-procedure benzodiazepine or narcotic.
- (4) Has any of the following medical conditions:
  - a. Inner ear, bariatric or eye surgery within the last 2 weeks,
  - b. Current emphysematous blebs,
  - c. Severe B-12 deficiency.
  - d. Bleomycin chemotherapy within the past year.
  - e. Class III or higher heart failure.
  - f. Undergoing novel therapy for prostate cancer

#### B4. POSSIBLE BENEFITS

It is not possible to determine whether a subjects will directly benefit from participation. Patients receiving SANO may potentially experience decreased pain and anxiety when undergoing office prostate biopsy. Benefits would not be expected to occur for those patients in the placebo oxygen arm.

Taking part in the study will increase scientific knowledge regarding the ability of the inexpensive, commonly available agent to reduce procedural pain and anxiety. Moreover, as SANO is currently being used throughout the United States for prostate biopsies, this study may help us identify risks to SANO that are currently not known or described.

If there is a significant improvement in patient anxiety and pain with the nitrous oxide, this could lead to changes in the standard of care for patients undergoing prostate biopsy.

We also may be able to identify patient factors that in the future allow us to prospectively identify patients who would be expected to experience more benefits from nitrous oxide. At the same time, this may allow us to identify patients who would not have significant benefit and might minimize their risk of exposure to nitrous oxide.

There is potential to also extend knowledge obtained in this study to other commonly performed office procedures that are associated with pain and anxiety, such as LEEPs, vasectomies, cystoscopies, and others.

#### B5. POSSIBLE RISKS AND ANALYSIS OF RISK/BENEFIT RATIO

##### Risks related to the use of questionnaires

Minimal risks associated with the completion of questionnaires include subject fatigue and the possibility of increased anxiety in answering questions about baseline pain and pain related to the procedure. Subjects will be informed that they are free to discontinue their participation in the study at any time should they choose.

##### Risks related to Nitrous Oxide administration

Nitrous oxide is a well-known drug used in medicine for anesthetic and analgesic purposes since 1844. Its use during labor has been shown to be safe and effective, with no known long-term effects on the mother and no known effects on the infant. There are known long-term effects of environmental exposure to nitrous oxide, including infertility, when not using a scavenger system for the escaped environmental nitrous oxide. The Miniscav® nitrous waste gas evacuation pump has been FDA-approved for use in medical offices with the Nitrouseal® system. We will not be using the Nitrouseal® and Miniscav® nitrous waste gas evacuation pump in any capacity that is not already approved by the FDA.

Nitrous oxide does have a risk of nausea and vomiting. The reported rates have been reported as high as 13% in literature, however these are at higher concentration of nitrous oxide and with longer durations. The reported vomiting risk with the Nitrouseal® system is <0.5%. For the procedure, the patient is maintained in the lateral position, which should minimize any aspiration risk. Sweating, drowsiness, lightheadedness, tachycardia and facial flushing has also been reported. The patients are routinely monitored after the prostate biopsy procedure, and any ill effects of the procedure itself or of the nitrous oxide will be assessed and cared for by our study team and clinical staff. Some adults may feel a sense of panic at higher concentrations (60-70%) than we will be using in our study (40%).

Finally, as with any inhaled gas, there can be a concern of hypoxia or apnea with administration of nitrous oxide. This event has not been routinely reported in the literature as a risk or side effect of nitrous oxide. However, this will be one of the side effects that we will be most interested in following. During the procedure, patients will undergo continuous oxygen saturation and heart rate monitoring. These values will be documented in REDCap as part of the patient's study records.

If there are concerns of hypoxia, either objectively by the oxygen monitoring or subjectively by the patient, the protocol will be to immediately turn off the nitrous oxide and administer 100% oxygen until vitals return to baseline. All personnel in the room will have BLS training. The Shapiro Surgical Clinic has a code cart which is readily available. In addition, the clinic is in close physical proximity to the operating rooms, with anesthesiologists responding to Code Blues in the building.

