### **Periprocedural Intervention**

The patient will be moved to the biopsy room and standard procedure for lateral positioning and explaining prostate biopsy will be done in the routine manner preferred by the individual Urologist. Oxygen saturation monitor will be applied to the patient's finger and monitored throughout the procedure. The patient's heart rate will also be monitored accordingly.

The inhalation gas mask will be positioned on the patient's face, and the patient will then be instructed to begin breathing as previously instructed. Initially the patient will receive 100% oxygen at 10 Liters/minute. In the control group, this will be continued throughout the procedure.

After the Urologist describes the procedure, the SANO group will have nitrous oxide turned on to 30%, ensuring that the patient is relaxed but still conversant through the procedure. The nitrous will be adjust up or down based on the patient's response to the question "are you feeling the nitrous" and "are you happy at this level". The range will be between 25 - 45%. This may take 2-3 minutes. Both groups will be asked these questions. Both groups will be asked to take several deep breaths before inserting the rectal probe. The prostate biopsy for both study and control participants will include the normal routine administration of local peri-prostatic nerve block using preferred technique of the individual Urologist. During the procedure, the patient and patient's oxygen saturation will be monitored by a [name], APP, or MD (separate from MD performing the procedure) and if at any point in time the patient is unhappy with gas inhalation, the observer will aid the patient in removing the mask. At the end of the procedure, the SANO group will be turned down to 0% nitrous oxide, and 100% oxygen will be administered through the mask for an additional 2-3 minutes as the patient is cleaned up and repositioned to the supine position. Assessment of the "time in" and "time out" of the procedure room will be recorded.

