### **Measuring gas flow:**

Maximum flow for this system is 19 L / min. The amount of gas flow is adjusted to match the patient's minute ventilation in order to maintain the black inspiration bag (inhalation reservoir) on the

Flowmeter about 3/4 full during the procedure. This varies from patient to patient depending upon respiratory rate, and volume of each breath. Excess gas flow simply flows through the circuit and into the scavenger and has no effect on the patient.

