### **Periprocedural Data Collection**

After the biopsy, the patient will be moved to the recovery room for routine post-procedure vitals as well as completion of post-procedure STAI score and Situational Pain Catastrophizing Score (S-PCS) on a tablet computer. The S-PCS was derived from the Pain Catastrophizing Scale (PCS), a validated questionnaire used to measure catastrophic thinking associated with pain. We will also question for side effects of the nitrous oxide including nausea, vomiting, dizziness, drowsiness, with an option to enter “other” as a manual entry. An additional question of whether the patient feels comfortable driving home independently will be assessed.

Patients who do not have an escort planned after their biopsy will be asked to perform two hand-eye coordination tests after completion of post-procedure surveys. First, the participants will be verbally instructed to extend one arm in front of them, and place one finger to the tip of their nose. After, the Trail-making test Part B will be administered. This test has been promulgated by the American Medical Association to screen for driving fitness. The Trails-making Part B test will ask participants to connect numbers (1-13) to letters (A-L) randomly written on a page. This test is scored according to accuracy and time required to make the connections (Joseph, 2013). If the participant is unable to accurately complete these tests, additional recovery time will be required. The participant’s performance and disposition will be included in the documentation of study procedures performed during the visit.

The urologist who performed the biopsy procedure will be provided the Operator Survey to assess the ease of procedure.

Chart review will be performed to capture any unanticipated ED visits, admissions, or office visits for the 7 days following the procedure. We will also record any phone calls that are made by patients within 7 days of procedure that pertain to procedure concerns.

Lastly, participants who completed study procedures during their prostate biopsy will be asked to complete a survey 2-10 months following the study biopsy. This brief survey is designed to understand participant’s recollection of pain and anxiety during the biopsy. The survey is estimated to take 2-3 minutes to complete.

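### Early mask removal, nitrous shut-off and brief pauses in breathing are not among the listed outcomes, so the complication and practicality results of Aim 2 can miss them

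*Combined protocol and SAP*

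**What the plan says.** **Purpose.** B1 gives the rate of complications with SANO as one thing the trial is to assess. Under Specific Aims, Aim 2 expects few side effects. Data Analysis uses post-biopsy side effects and the ability to drive home as a stand-in for practicality in the clinic.

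**Event of interest.** B5, Risks related to Nitrous Oxide administration, says "there can be a concern of hypoxia or apnea with administration of nitrous oxide" and adds that "this will be one of the side effects that we will be most interested in following".

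**What is measured during the procedure.** The same section states: "During the procedure, patients will undergo continuous oxygen saturation and heart rate monitoring". It continues: "These values will be documented in REDCap as part of the patient's study records". Periprocedural Intervention adds a human observer: "During the procedure, the patient and patient's oxygen saturation will be monitored by a" clinician other than the operating urologist.

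**Gas.** Both arms start on 100% oxygen, and control stays on it. The SANO arm is set to 30% nitrous oxide and then adjusted within 25-45%. Under Measuring gas flow, "The amount of gas flow is adjusted to match the patient's minute ventilation", judged by how full the reservoir bag is.

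**Stopping the gas.** Under Periprocedural Intervention, "if at any point in time the patient is unhappy with gas inhalation, the observer will aid the patient in removing the mask". Pre-procedure Evaluation makes the same offer to the patient. B5 also describes turning off the nitrous oxide when hypoxia is a concern.

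**What is asked afterwards.** Periprocedural Data Collection asks about "side effects of the nitrous oxide including nausea, vomiting, dizziness, drowsiness, with an option to enter" anything else as free text.

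**The concern.** Two kinds of event bear on the safety and practicality conclusions but have no stated place in the data.

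The first is apnea. It is named beside hypoxia as an event to follow, but the documented values are saturation and heart rate. No respiratory rate, definition of apnea or recorded observation of breathing is mentioned. If saturation holds up through a short pause on oxygen-rich gas, the pause may go uncounted.

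The second is intolerance. A patient who has the mask taken off, or whose nitrous oxide is shut off, has shown plainly that the method did not suit him. The plan says what staff will do, but not that the event will be recorded or reported. A final report could then describe few side effects without saying how many patients stopped the gas early. Events inside the procedure room are hard to reconstruct reliably if nobody writes them down at the time.

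**Working it through.** **1. The plan's own figure.** The only sample-size calculation concerns the efficacy score. With a difference of 4, SD 8, power 80% and two-sided alpha 0.05 (sidedness is not stated, so two-sided is assumed), d = 4/8 = 0.5. A two-sample t-test then needs 63.77, so 64 per group. Allowing for 15% loss, 64/(1 - 0.15) = 75.3, so 76 per group and 2 x 76 = 152 in total. The stated numbers reproduce. They were not set with safety in mind, but they fix the denominator: 64 to 76 SANO patients.

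**2. Inspired oxygen.** The background (B2, Administration) describes nitrous oxide as mixed with oxygen. If the balance is all oxygen:

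- SANO at 25% nitrous oxide: 100 - 25 = 75% oxygen
- SANO at the 30% starting setting: 100 - 30 = 70% oxygen
- SANO at 45% nitrous oxide: 100 - 45 = 55% oxygen
- Control: 100% oxygen throughout

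So both arms breathe enriched gas. That enriched gas delays desaturation is general physiology, not a statement in the protocol, and I use it only to say that a brief apnea may be missed.

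**3. Each event traced through the plan.**

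| Event | Described in | Listed as recorded | Named in Data Analysis |
|---|---|---|---|
| Hypoxia | B5 | Yes, through saturation in REDCap; no threshold, duration or summary variable | No |
| Apnea | B5 | No respiratory variable | No |
| Mask removed | Pre-procedure Evaluation; Periprocedural Intervention | No | No |
| Nitrous oxide turned off early | B5 | No | No |
| Nausea, vomiting, dizziness, drowsiness | B5 (in part); Periprocedural Data Collection | Yes | Yes, as side effects |

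The room entry and exit times that are recorded do not show how long the gas was taken.

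**4. What a zero count would mean.** With no recorded events in n patients, the one-sided 95% upper limit is 1 - 0.05^(1/n):

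- n = 76: 1 - 0.05^(1/76) = 3.9%
- n = 64: 1 - 0.05^(1/64) = 4.6%

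This limit applies to the rate of recorded events. It carries over to the true rate only if every event is recorded. The documents give no detection rate, so the distance between the two cannot be computed.

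**The case against.** The case against is substantial.

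- **Hypoxia is measured.** Saturation is its direct measure, is continuous and goes into REDCap. A reader might infer that both named events can be missed. The documents do not support that: the measurement gap is for apnea only, and for hypoxia what is missing is a definition for analysis. This stands.
- **Apnea is not invisible to the plan.** A separate clinician watches the patient as well as the oximeter, the SANO patient is kept able to converse, and adverse events are reported to the review committee. It would be wrong to infer that the trial cannot detect apnea. These safeguards narrow the gap, but none gives a defined count by arm.
- **The arms differ in the other direction.** On the same physiological assumption, SANO patients have less oxygen in reserve than controls, so a pause would show sooner with SANO. The documents give no ground for saying that the oxygen difference hides SANO harm relative to control.
- **There is no formal safety endpoint.** The plan states an aim about complications, and hypoxia or apnea is one of several side effects of interest. The primary outcome is anxiety and pain.
- **The symptom list.** A reader might go on to fault it for not prompting panic, sweating or flushing. B5 ties panic to concentrations of 60-70%, above the range used here, and the list has a free-text entry for the rest. I do not press this.
- **The forms are not in the documents.** The REDCap case report form is not included and the flowchart is not shown, so a field for mask removal may already exist. If it does, the remaining step is to name it in the protocol and in the analysis.

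**Conclusion.** The concern holds in a narrow form. The text lists no record of early mask removal, early shut-off of nitrous oxide or observed pauses in breathing, and it plans no analysis of them. The complication and practicality conclusions of Aim 2 can therefore miss them. The point about early stopping follows from the text alone. The point about apnea also assumes that the balance gas is oxygen and that enriched oxygen can mask a short pause.

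The gap cannot be sized. It is tempting to scale the zero-event limit by an assumed detection rate, but any such rate would come from outside the documents. The comparison of anxiety and pain scores is not in question. This is a minor improvement, worth making because the information is cheap to collect at the time and hard to recover later.

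**What to change.** Add fields to the REDCap procedure form, completed in both arms by the observer already in the room:

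- mask removed or gas stopped early: yes/no, time, reason
- any observed pause in breathing: yes/no, using a definition that the investigator sets before enrolment

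Name both under Periprocedural Data Collection. Under Data Analysis, report them by randomised arm with the Aim 2 side-effect results, as counts out of all patients who started the gas. If the form already holds such fields, only these two sections need the addition.

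This is recording only. It changes no monitoring, stopping or management rule and needs no new equipment or staff. The cost is slightly more recording for the observer. Because only the patient is stated to be blinded, that observer may know the arm, and a visible pause is a crude measure of apnea. The report should state both limits.

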### **Possible Unauthorized Use of Nitrous Oxide**

Inhalation of nitrous oxide is used/abused in recreational settings with the purpose of causing euphoria and hallucinations. To prevent potential misuse, the nitrous oxide will be stored within the operating room storage area reserved for anesthetic gases during non-office hours.

### **Potential for Loss of Confidentiality**

There is a potential for loss of confidentiality for participants in the study. Protections will be implemented to mitigate this risk. As detailed in our protocol, we will use REDCap to collect patient information and questionnaires. Though REDCap is generally considered secure for the purposes of PHI, it is a web-based application and the data is accessible to study team members on their own personal computers. Access to our REDCap will only be limited to study team members who are trained in protecting PHI. . Any electronic study files or information that is not stored on REDCap will be kept on a secure directory on the BIDMC server that is only accessible to research staff.

Only summaries of group data will be reported in any publications or presentations, with no identification of individuals. These precautions should serve to protect PHI in accordance with HIPPA regulations.

### **Reporting of Adverse Events**

All adverse events will be reported to the BIDMC Human Research Committee promptly in accordance with guidelines.

### **Analysis of Risk/Benefit Ratio**

Based on the above risks, the principal investigator views this study as moderate risk. With the precautions and procedures to minimize risk as described in this section, we anticipate minimal complications and discomfort. In light of the study's potential benefits, the principal investigator believes the risk:benefit ratio to be favorable.

## **B6. RECRUITMENT AND CONSENT PROCEDURES**

### **Recruitment**

The primary Urologist will introduce the SANO study to the patient and provide an informational handout at the time they discuss prostate biopsy with the patient. After the Urologist has discussed and planned for prostate needle biopsy, the study team will examine the list of scheduled biopsies for the week, and a baseline examination by the clinical team for eligibility verification will be performed through a medical record review by a trained member of the research staff.

. Those patients who meet criteria will be reviewed by their Urology Attending for appropriateness of study and will provide authorization to contact eligible subjects. Eligible patients will be sent a secure message via PatientSite ([See Template Introductory Letter](#)) to introduce the study. In addition, the patient will be called on their preferred clinical contact phone number by a study team member. The study team member will follow a templated introductory contact script ([See Template Introductory Contact Script](#)). In attempting to reach the patient, and in accordance with BIDMC Human Research procedure, no more than ten (10) phone attempts will be performed, and all calls will take place between 10am-9pm Monday thru Friday, and 10am – 5pm Saturday and Sunday. If there is no answer, study team member will leave a templated contact script ([See Template No Answer Contact Script](#)).

To assess interest in completing the post-biopsy survey, a letter will be sent to introduce the survey to participants who completed study procedures during their study biopsy (see Re-contact Letter script). We will wait for one week before further outreach to patient. For participants registered on PatientSite, a REDCap survey link will be sent via secure PatientSite message (see Re-contact PatientSite script). For participants who do not prefer PatientSite, we will call the patient directly (see Re-contact Telephone script). Patients will be asked to complete the survey via a REDCap link sent to the patient's email. If the patient prefers, we will offer the option to complete the survey questions over the phone . No more than three phone attempts will be performed, and all calls will take place between 10am – 9pm Monday-Friday, and 10am – 5pm Saturday and Sunday. If there is no answer, the study staff member will leave a templated voicemail (see Recontact Voicemail script).

In the event that individuals contacted are distressed in any way by the contact, we will contact the patient's Urology Attending, who will either personally reach out to the patient to alleviate

their concerns or have a designated team member reach out to the patient to alleviate their concerns.

### **Consent**

Informed consent will be obtained for all participants who are potential study candidates. A qualified member of the research team will review the informed consent form with all patients who express interest in the study. The subject will be allowed to ask questions at any point. Study personnel will explain that the subject is free to refuse participation in this research study and that. All patients who agree to participate will be asked to sign the ICF electronically through REDCap. Consent will be obtained before any study-specific tests or procedures are performed. Study personnel will document the consent process. Subjects will be provided an electronic copy of the signed ICF.

